## **1.2 Study objectives and endpoints**

Objectives:

Primary

- Renal function assessed as glomerula filtration rate (GFR) – MDRD formula – 18 months after heart transplantation

Secondary

- To assess occurrence of treatment failures up to or at Month 18 post Tx, while treatment failure is defined as a composite endpoint of biopsy proven acute rejection of ISHLT 1990 grade  $\geq 3A$  (ISHLT 2004 grade  $\geq 2R$ ), acute rejection episodes associated with hemodynamic compromise, graft loss / re-transplant, death, loss to follow-up (at least one condition must be present)

- To assess incidence of MACE and each of its components at Month 18 post Tx
- To assess renal function by GFR – Cockcroft-Gault method – at Month 12 and 18 post Tx
- To assess renal function (serum creatinine) and evolution of renal function between Month 6 and Month 18 post Tx (creatinine slope)
- To assess safety and tolerability at Month 6, 9 and 18 post Tx (acc. to safety parameters specified in section 7.6 of the protocol)

## 2 Statistical methods

### 2.1 Data analysis general information

All statistical analyses were performed [REDACTED]

[REDACTED] Analysis was carried out using the SAS (Statistial Analysis System) software, version 9.2, 2009, SAS Institute Inc., Cary, North Carolina, USA.

Analyses were done when all patients had completed the trial at 18 months post Tx (or discontinued prematurely).

The following periods were considered for analyses:

- The primary analysis of renal safety and tolerability concerns the **period of randomized treatment** between Month 6 (baseline) and Month 18 or the last assessment within this period in the event of a patient's premature discontinuation from the study. If indicated, e.g. for analysis of renal function and type and frequency of adverse events, the period from Month 6 to Month 18 was portioned into (a) the **switch period** between Month 6 and Month 9 and (b) the **maintenance period** between Months 9 and 18 after Tx.
- As a separate study period, the initial 3 months period between Screening and Baseline visit (**run-in period**) was analyzed with regard to treatment, efficacy, and safety of the immunosuppressive regimen.

In patients who discontinued prematurely from the study, the last available information under study treatmentwas analyzed.

Adverse events were analyzed separately for the initial 3 months period between Screening and Baseline visit (**Run-in period**) and for the randomized treatment period between Baseline visit (Month 6) and Month 18.

Significant events like rejection episodes, hemodynamic compromise, and MACE were additionally analyzed for the period between transplantation and Screening (Month 3 post Tx) (**Pre-screening period**).

Unless otherwise stated, all statistical tests were two-sided and used the 0.05 level of statistical significance. All summary statistics were presented by treatment group. Frequency distributions were provided for categorical variables. Descriptive statistics of mean, standard deviation, minimum, median and maximum were presented for continuous variables. Time to event data including rates of affected patients were assessed by Kaplan-Meier statistics and compared between the two groups with the logrank test.

Data from all centers that participated in this study were combined and the factor center was included in the analysis of the primary endpoint.

### **2.1.1 General definitions**

#### Study drug:

The term “Study drug” refers to any drug administered to the patient as part of the required study procedures.

Certican®/ Everolimus was investigational drug. Sandimmun®Optoral/Cyclosporin A, Prograf®/Tacrolimus and MPAs (Myfortic®/EC-MPS or CellCept®/MMF) were considered as study drug as well. Corticosteroids were handled in the same way as concomitant medication.

#### Date of first administration of study drug:

“Date of first administration of study drug” is defined as the first intake of study medication which should start within 5 days preceding the Screening visit and be documented on the Everolimus therapies CRF.

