The primary objective of this trial is to demonstrate superiority of a CNI-free regimen with respect to the renal function at Month 18 post Tx assessed by glomerular filtration rate – MDRD method – as compared to the standard CNI-based regimen in heart transplant patients.

Secondary objectives of this trial are:

- to assess occurrence of treatment failures up to or at Month 18 post Tx, while treatment failure is defined as a composite endpoint of biopsy proven acute rejection of ISHLT 1990 grade \geq 3A (ISHLT 2004 grade \geq 2R), acute rejection episodes associated with hemodynamic compromise, graft loss / re-transplant, death, loss to follow up (at least one condition must be present)
- to assess incidence of MACE and each of its components at Month 18 post Tx
- to assess renal function by glomerular filtration rate - Cockcroft-Gault method - at Month 12 and 18 post Tx
- to assess renal function (serum creatinine) and evolution of renal function between Month 6 and 18 post Tx (creatinine slope)
- to assess safety and tolerability at Month 6, 9 and 18 post Tx (according to safety parameters specified in [section 7.6](#))

4 Study design

This is a prospective, multi-center, randomized, controlled, parallel group, open label study in heart transplant recipients. A total of 200 patients fulfilling the inclusion and exclusion criteria at Baseline visit (Month 6 post Tx) will be randomized to the two treatment groups. Enrollment will be continued until the required sample size is achieved.

Once consent is obtained, screening data will be collected to determine each patient's eligibility for study participation. Screening assessment will be performed at Month 3 post Tx and relevant data from transplantation will be recorded retrospectively.

During the first three months post Tx the patients may be treated according to center standards. Latest after study inclusion (Month 3 post Tx ± 2 weeks), the patients should receive an immunosuppressive regimen consisting of Cyclosporin A (based on C0-h level) or Tacrolimus (based on C0-h level) + Everolimus (target C0-h level: 5 – 10 ng/mL) or MPA + corticosteroids.

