6.2 Treatment groups

The day after Screening visit, during the run in phase, all patients will receive the following immunosuppressive therapy:

Cyclosporin A (C0level: 100-200 ng/mL) or Tacrolimus (C0level: 5 - 10 ng/mL) and Everolimus (C0level: 5-10 ng/mL) or MPA and corticosteroids.

At Baseline visit (Month 6 post Tx) patients will be assigned to one of the following two treatment groups in a ratio of 1:1:

- **Maintenance** of immunosuppressive **CNI-based regimen** (CNI group):
Cyclosporin A (C0: 50 – 150 ng/mL) or Tacrolimus (C0: 3 – 8 ng/mL)+
Everolimus (C0: 5 – 10 ng/mL) +
Corticosteroids
- **Switch to CNI-free regimen** (CNI-free group):
MPA (MMF 1500 - 3000 mg/day OR EC-MPS 1440 - 2880 mg/day) +
Everolimus (C0: 5 – 10 ng/mL) +
Corticosteroids +
Cyclosporin A ≤ 75 ng/mL (according to -evel) (months 6-9) or Tacrolimus ≤ 5 ng/mL (according to C0) (months 6-9)

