10.4 Study treatments

10.4.1 Study medication

Study medication is Everolimus, RAD001); the other components of the immunosuppressive regimens are considered as concomitant medication.

Duration (days) of Everolimus, study medication application will be summarized. Dosage averages will be calculated including and excluding zero doses for periods of temporary interruption of study medication regardless of whether this was due to safety reasons or patients' non-compliance. Daily Everolimus, dose levels will be summarized with mean, standard deviation, minimum, median, and maximum by time interval. Frequency of dose reduction (including temporary dose interruption) for safety reasons as per protocol guidelines as well as average daily dose will be presented by visit. Reasons for dose adjustments (including temporary dose

interruption) will be presented by frequency distribution. Permanent treatment discontinuations will be analyzed by frequencies.

These analyses will be performed per treatment group, for the ITT- and the PP population and related to the study phases (see [section 10.1](#)).

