2. Randomization (Baseline Visit – Month 6 post Tx): At day of randomization, the site provided the information of eligible patient to the CRO by fax. The CRO randomization department allocated the patient the next free consecutive randomization number allocated to the site. Randomization number and allocated treatment (according to the randomization list) were provided to the site by fax.

Patients then either received an immunosuppressive regimen consisting of a CNI (Tacrolimus or Cyclosporin A) with Everolimus with corticosteroids or were switched to the CNI-free regimen in the following way:

Starting the day following the Month 6 assessment, Cyclosporin A was reduced to  $\leq 75$  ng/mL (according to C0 level) or Tacrolimus was reduced to  $\leq 5$  ng/mL (according to C0 level) for 8 weeks and subsequently removed completely. Depending on the initial immunosuppression either MPA or Everolimus was added to the patient's immunosuppressive regimen.

Consequently, patients received a transitional immunosuppressive regimen of Cyclosporin A or Tacrolimus and Everolimus and MPA or MMF until complete switch to the CNI-free regimen was achieved at 9 months post Tx.

Dose increase / adjustment of MPA was performed based on the investigator's experience and the given clinical conditions, adverse events, etc. The CNI-free regimen was achieved after a maximum of 3 months and was stable by Month 9. During the therapy-switch a control assessment was performed at Month 8.

In all patients, further control assessments were performed at Month 9, 10, 12 and 18 (end of study and early discontinuation) post Tx.

Corticosteroids were added to the immunosuppressive regimen in all patients, according to local standard. A dose of 0.05 – 0.3 mg/kg prednisolone or equivalent were continued throughout the whole study.

Obligatory biopsies were obtained at Month 6, 9, 12, 18. Facultatively biopsies may have been obtained at every study visit.

Statistical analysis and report writing was performed when all patients had completed Month 18 after Tx assessment.

The primary analysis of renal safety and tolerability concerned the period of randomized treatment between Month 6 (baseline) and Month 18 or the last assessment within this period in the event of a patient's premature discontinuation from the study.

No interim analysis was conducted.

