## **2.4 Treatments (study treatment, rescue medication, concomitant therapies, compliance)**

### **2.4.1 Study treatment / compliance**

Duration (days) of Everolimus application were summarized. Dose interruptions, i.e. days with dose of 0 mg were considered for calculation of duration. Daily Everolimus dose levels were summarized with mean, standard deviation, minimum, median, and maximum by visit. Dosage averages were calculated including and excluding zero doses for periods of temporary interruption of study medication regardless of whether this was due to safety reasons or patients' non-compliance. Assignment of the DAR records to the visits were calculated based on the visit dates. Reasons for dose adjustments (including temporary dose interruption) were presented by frequency distribution. These frequencies of dose reduction (including temporary dose interruption) for safety reasons as per protocol guidelines were presented by study period. Permanent treatment discontinuations were analyzed by frequencies.

These analyses were performed per treatment group, for the SAF population and related to the study periods in the randomized treatment period (see section 2.1 Data analysis general information). For the run-in period, duration and mean daily dose were summarized for the ENR population displaying both, randomized versus not randomized patients as well as the initial treatment groups CNI+MPA versus CNI+ Everolimus

Daily Cyclosporin A and Tacrolimus doses adjusted by the patients' visit-specific body weight and MPA doses were summarized by visit and in the same way as Everolimus. Data were presented separately for each treatment group. Induction therapy (Basiliximab or ATG or no induction) received by patient was summarized by treatment group, for the SAF population. The distribution of the specific CNI medications was summarized by treatment group.

Duration (days) of treatment with Cyclosporin A, Tacrolimus, MPA, and steroids as well as frequency of Cyclosporin A, Tacrolimus and MPA dose adjustments (including temporary dose interruption) for safety reasons as per protocol guidelines were determined. Reasons for dose adjustments (including temporary dose interruption) were presented by frequency distribution. Permanent treatment discontinuations were analyzed using frequency distribution. All other immunosuppressive therapies were summarized by ATC (Anatomical, Therapeutic, Chemical) classes.

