### **5.2.2 AE date imputation**

In case of missing or partial start date or end date of an AE, the start date should be shifted to the earliest possible date, but not earlier than the first intake of study drug while the end date should be shifted as far back as possible.

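### The SAP's first-dose date comes from the everolimus form, so in CNI+MPA entrants run-in events and medications with incomplete start dates are imputed about 13 weeks late

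*SAP*

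**What the plan says.** SAP 2.1.1 names everolimus as the investigational drug and adds that cyclosporin, tacrolimus and the MPA products "were considered as study drug as well". The next definition, the date of first administration of study drug, is the "first intake of study medication which should start within 5 days preceding the Screening visit and be documented on the Everolimus therapies CRF". No other form is named, and no fallback is given for a patient without an everolimus record at that time.

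The run-in does not require everolimus. Protocol section 4 sets the regimen from Month 3 as a CNI with everolimus "or MPA + corticosteroids". SAP 1.1 describes what follows for patients switched to the CNI-free regimen: "Depending on the initial immunosuppression either MPA or Everolimus was added" to their treatment. SAP 2.4.1 plans run-in exposure tables for "the initial treatment groups CNI+MPA versus CNI+ Everolimus".

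SAP 5.2.2 moves a missing or partial adverse event start to the earliest possible date, "but not earlier than the first intake of study drug". SAP 5.2.3 (concomitant medication) and 5.2.3.2 (post therapies) set the same limit. SAP 5.2.1, for study drug records, uses the Screening visit instead.

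**The concern.** The two neighbouring definitions in SAP 2.1.1 do not fit together for one permitted entry group. A CNI+MPA entrant is on study drug from Screening under the first definition, but has no first-administration date until everolimus starts under the second. That date is then used as a lower limit for imputed start dates, so the mismatch changes results.

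The tables at stake are those that separate the run-in from the randomized treatment period. SAP 2.7.1 reports safety by period, and the switch period (Month 6 to Month 9) is where a reader would look for problems with conversion. Run-in records with incomplete dates would appear there for one entry group, while the same records would stay in the run-in for the other.

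**Working it through.** The plan states no figure to reproduce. The check sets the definitions side by side and sizes the date shift by calendar arithmetic.

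**Step 1. When does a CNI+MPA entrant first take everolimus?**
- CNI-free arm: the missing component is added from the day after randomization at Month 6 (Protocol 6.5.1; SAP 1.1).
- CNI arm: Protocol Table 6-1 shows everolimus at target level and no MPA after Month 6.
- Not randomized: no protocol step introduces everolimus, so the date may not exist. SAP 2.7.1 nevertheless includes these patients in the run-in adverse event summaries.

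**Step 2. How late is the date?**
- Inputs: Screening at Month 3 ± 2 weeks and Baseline at Month 6 ± 1 week (Protocol section 7); one month = 365.25/12 days.
- Nominal gap: 3 × 365.25/12 = 91.3 days, or 91.3/7 = 13.0 weeks.
- Shortest gap (Screening 14 days late, Baseline 7 days early): 91.3 − 21 = 70.3 days.
- Longest gap (Screening 14 days early, Baseline 7 days late): 91.3 + 21 = 112.3 days.
- In the CNI-free arm everolimus starts one day after that at the earliest.

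**Step 3. What does the imputation rule do?** Take an illustrative CNI+MPA entrant with Screening on 2 April, Baseline on 2 July (91 days later) and first everolimus on 3 July.

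| Run-in adverse event record | Result under SAP 5.2.2 | Consequence |
|---|---|---|
| Start wholly missing | 3 July | Falls in the switch period |
| Start known only as May | Earliest date in May is 1 May; the limit is 3 July | The limit contradicts the recorded month |
| Start missing, end date in May | 3 July | Start falls after end |
| Start fully recorded in May | No imputation | Stays in the run-in |

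For a CNI+everolimus entrant with the same Screening date, the limit lies at about Screening. The first three records then stay in the run-in. The concomitant and post therapy rules work the same way. The prior therapy rule (SAP 5.2.3.1) is worded differently and is not relied on here.

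**Step 4. What does not depend on this date?**
- SAP 5.1.1 bounds the study periods by visits, not by first dose.
- SAP 2.7.1 shows all adverse events in the run-in summaries and counts relative onset day from the initial dose in each period.
- SAP 2.6.2 starts event times at randomization.
- SAP 2.5.2 compares Month 18 GFR adjusted for Month 6 GFR.

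**Step 5. How many records?** The documents give neither the share of CNI+MPA entrants nor the number of incomplete dates. Assuming a share would count patients with a late date, not records that change, so no count is offered.

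**The case against.** One defence is that the everolimus date is intended. Protocol 10.4.1 treats everolimus as the study medication and says "the other components of the immunosuppressive regimens are considered as concomitant medication". That explains the choice of form but does not rescue the rule: SAP 2.1.1 widens the term study drug, and an everolimus date is still unusable as a limit for run-in records in patients not taking everolimus.

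A second defence is that the effect is small, and this largely stands. The protocol collects adverse event start and end dates (7.6) and queries omissions (9.3). The run-in regimen is fixed before randomization, so any shift should balance between arms in expectation. The error is between periods, not clearly between arms.

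A reader might infer more than the documents support:

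- **That run-in adverse events are misplaced in general.** They are not. A fully dated event is allocated by visit dates and tabulated whatever the first-dose date.
- **That run-in events lose treatment-emergent status.** The SAP uses the term (2.7.1, 2.7.2 and the infection definition in 5.1.3) but does not define it. An effect would follow only if it were keyed to the everolimus date, which no text says.
- **That drugs stopped in the run-in become prior medication.** The imputation sections do not classify drugs, and SAP 2.4.2 summarises concomitant medication by study period.
- **That the plan has three conflicting start rules.** Protocol 6.2 says "The day after Screening visit, during the run in phase, all patients will receive the following immunosuppressive therapy", SAP 2.1.1 refers to the 5 days before Screening, and SAP 5.2.1 uses Screening. These serve different purposes: a required regimen, a window matching the start of dose recording in Protocol 7.4, and a limit for incomplete dosing dates. Protocol 6.5.1 also allows everolimus before Visit 1.

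**Conclusion.** The definition is wrong as written for CNI+MPA entrants. This is more than missing detail: following the SAP literally moves a wholly undated run-in adverse event or medication about 91 days (range 70 to 112) into the randomized period. A partly dated record, or one with a known end date in the run-in, gets a start that contradicts the data. A non-randomized CNI+MPA entrant may have no limit at all.

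This assumes that these patients stay on CNI+MPA until Month 6, as SAP 1.1 and Protocol Table 6-1 imply, and that the first-intake limit in SAP 5.2 means the date defined in SAP 2.1.1, the only such date defined. Severity is minor: only descriptive safety and medication tables are affected, and the number of records is unknown.

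**What to change.** - In SAP 2.1.1, define first administration for every patient as the earliest dose, on or after the Screening visit, of any protocol immunosuppressant (CNI, everolimus or MPA), read from all dosage forms. This agrees with the SAP's own scope of study drug and with the Screening limit in 5.2.1.
- Use that date as the limit in SAP 5.2.2, 5.2.3 and 5.2.3.2.
- Add that an imputed start may never override a known month or fall after a known end date.
- Leave the start of the randomized treatment period at Visit 2/Baseline, as in SAP 5.1.1.

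The cost is one revised definition, one added sentence and one derived date. No new data are needed, because Protocol 7.4 already records all immunosuppressant dosing from 5 days before Screening.

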#### Baseline:

“Baseline” in the sense of “baseline value” means all values collected at Baseline visit at month 6 or, if not available, the corresponding value collected at Screening visit.

#### Last contact:

Last date a contact with the patient is documented, e.g. date of study visit, telephone call, letter, etc.

## **2.2 Analysis sets**

The **Enrolled Patient Population (ENR)** includes all patients who signed an informed consent regardless whether they received study treatment or not.

The **Safety Population (SAF)** consists of all patients who signed an informed consent and who were treated with at least one dose of any immunosuppressive medication after the Screening visit. Note: The statement that a patient had no adverse events constitutes a safety assessment.

The **Randomized Population (RAN)** is defined by all patients who were randomized at Baseline visit. This population will also include patients who were randomized but not treated with the randomized medication.

The **Full Analysis Set (FAS)** consists of all randomized patients who received at least one dose of any immunosuppressive therapy after Baseline Visit (Month 6) and have at least one

post-baseline assessment of the primary outcome variable (renal function based on MDRD method). Randomized patients without data on the primary outcome variable will be excluded from this population; their data will be analyzed for the initial treatment period (up to Month 6) and within the RAN and SAF. Following the intent-to-treat principle, patients will be analyzed according to the treatment group they were assigned to at randomization.

The **Per-protocol Population (PP)** consists of all FAS patients who did not show major deviations from the protocol procedures that may have an impact on the study outcome and who have completed the treatment period at Month 18 according to protocol. Criteria that are assumed to have such an impact were defined before analysis during the Blind Review Meeting and are documented in the Appendix, section 5.6 Rule of exclusion criteria of analysis sets.

For the period before Baseline visit (Month 6) the enrolled patient population was divided by randomization status into randomized patients and not randomized patients.

## **2.2.1 Subgroup of interest**

## **2.3 Patient disposition, demographics and other baseline characteristics**

Demographic and background information was summarized for the ENR-, the SAF- and the FAS - Population, using frequency distributions for categorical variables and descriptive statistics of mean, standard deviation, minimum, median and maximum for continuous variables. Background information included prior medication, past/current medical conditions and transplant history.

Medical history was coded using MedDRA and was presented by system organ class, MedDRA preferred term and treatment group. Separate tables were provided for past medical condition and current medical condition. Prior medication was coded according to WHO Drug Reference List.

In addition to these variables which were evaluated at Screening (Visit 1, Month 3 post Tx), the course of renal function (GFR) as well as efficacy variables (treated acute rejection, biopsy proven acute rejection of ISHLT 1990 grade  $\geq 3A$  resp. ISHLT 2004 grade  $\geq 2R$ , acute rejection associated with hemodynamic compromise, graft loss / re-transplantation, death) were determined and properly described for the run-in period between Screening (Visit 1, Month 3 post Tx) and Baseline (Visits 2, Month 6 post Tx).

The two treatment groups were compared descriptively with respect to these variables.

No formal statistical testing was conducted for comparability purposes.

